4 STUDY DESIGN

4.1 Description

This is a Phase 2, double-blinded, placebo-controlled trial assessing the safety of Q-Urol use after brachytherapy placement in patients with localized prostate cancer. Patients will be randomized in a 1:1 ratio to receive Q-Urol/Placebo twice daily for six weeks after brachytherapy placement. Questionnaires will be administered pre- and post-treatment to assess the change in prostatitis symptoms and quality of life measures. The mean values between groups will be compared.

Once 42 patients (21 to each arm) have been enrolled and treated on the study therapy, enrollment will be placed on hold and an interim analysis conducted. The interim analysis will be conducted for futility and efficacy and will be reviewed by the DSMC. If the analysis is favorable, as defined in the Statistical Analysis section, the trial will open to the enrollment of 98 additional subjects, 49 per arm. However, if the analysis does not demonstrate standards defined in the statistical analysis, the trial will be closed to accrual.

Version Date: 11APR2023

Safety monitoring will be overseen by the DSMC at HCI. See Section 12.4 for safety monitoring plan and early stopping rules.

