4.2 Randomization and Blinding

Patients who meet all criteria for enrollment will be randomly assigned to receive Q-Urol (Arm 1) or placebo (Arm 2). Patients will be randomized through the OnCore system in a 1:1 ratio to Arm 1 or Arm 2 and stratified by dose level of brachytherapy used.

To preserve the blind, only the Investigational Drug Services Pharmacy personnel and Data Safety Monitoring Committee (DSMC) at Huntsman Cancer Institute will know treatment assignments. Access to unblinded data/documents will be controlled by the pharmacy to ensure the blind is maintained. Every effort will be made to blind the patient, the investigator, and the study team to the treatment assignment, but the inadvertent unblinding of a patient may occur. If an investigator, site personnel, or patient is inadvertently unblinded, the unblinding will not be sufficient cause for the patient to be discontinued from study treatment or excluded from study analyses. Cases of accidental unblinding will be recorded in the applicable eCRF and evaluated by the DSMC for appropriateness of inclusion in the study analysis.

In the case of an emergency, the treating investigator has the sole responsibility for determining if unblinding of a patient's treatment assignment is warranted. Patient safety must always be the first consideration in making such a determination. If the treating investigator decides that unblinding is warranted, the investigator should contact the investigational pharmacy for treatment assignment.

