7.2 O-Urol and Identical Placebo

7.2.1 How Supplied, Stored, Packaged, and Labeled

Q-Urol will be provided by Farr Laboratories. Q-Urol will be provided as 375 mg proprietary blend and 37.5 mg calcium capsules for oral administration. They should be stored at room temperature, away from heat, moisture, and direct light.

Placebo capsules, which do not contain the active ingredients of Q-Urol, will be compounded by the Investigational Drug Services Pharmacy at Huntsman Cancer Institute and will be identical in appearance to Q-Urol.

The Investigator, or an approved representative, will ensure that all investigational products are stored in a secured area with controlled access under required storage conditions and in accordance with applicable regulatory requirements.

According to Farr labs, the Q-Urol is manufactured in laboratories with Current Good Manufacturing Practice regulations enforced by the FDA. In addition, Farr Laboratories ensures consistency and purity via the following measures:

Version Date: 11APR2023

 Ensures that the Certificates of Analysis (CofA's) are in compliance with the United States Pharmacopeia (USP) standards on Identification and Purity Controls

- Monitor manufacturing and quality control product documentation
- Conduct laboratory testing on Finished products for Microbio, Heavy Metals, and Residual Solvents

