12.3.2 Evaluable for response

A modified intent-to-treat data set will be used to assess efficacy. Subjects who have successfully undergone brachytherapy and received one dose of Q-Urol will be evaluable for response. Subjects who fail to undergo brachytherapy or begin Q-Urol therapy will be replaced. Those who do not complete the end of treatment patient questionnaires will be considered treatment failures.

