13.2 Statistical Analyses

13.2.1 Sample size determination

The outcome for sample size determination is the primary endpoint variable, the peak of the National Institutes of Health-Chronic Prostatitis Symptom Index (NIH-CPSI) total score measured from baseline to six weeks post brachytherapy. The primary hypothesis is that the mean of the primary outcome variable will be $\frac{1}{2}$ standard deviation lower in patients taking Q-Urol compared to placebo. A single interim analysis is planned after N1= 21 subjects per group have outcome data. The interim and final analysis will compare the treatment and control means using nominal t statistics (control minus treatment). If the t statistic has a value less than -1.16 at the interim analysis the trial will be terminated for futility. If the t statistic has a value greater than 2.85 at the interim analysis the trial will be terminated for efficacy.

If the study is not terminated for efficacy or futility at the interim analysis an additional N2 = 49 patients per group will be accrued for a total of N = 70 patients per group. If the interim analysis is done at the planned sample size (21 patients per group) the treatment will be deemed efficacious at the final analysis if the t statistic has a nominal value greater than 1.67.

The above design was evaluated using 100,000 simulated data sets for both the null and alternative hypotheses. There is 90% power at overall one-sided Type I error equal to 0.05 (one-sided) to detect a 0.5 standard deviation lower mean of the primary endpoint in the treatment group compared to the control group. The probability of early termination for futility under the null hypothesis is 12%. The probability of early termination for futility under the alternative hypothesis is 0.3%. The probability of early termination for efficacy under the alternative hypothesis is 12%.

If the interim analysis or final analysis is performed at a sample size that is different than the planned sample size the final analysis will be adjusted to maintain an overall Type I error of no more than 0.05 (one-sided).

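### Section 4.2 has a DSMC that knows treatment assignments judge whether accidentally unblinded patients are analysed, with no criteria in the documents reviewed

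*Combined protocol and SAP*

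**What the plan says.** Section 4.2 makes three statements that bear on this point:

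- On who is unblinded by design: "only the Investigational Drug Services Pharmacy personnel and Data Safety Monitoring Committee (DSMC) at Huntsman Cancer Institute will know treatment assignments".
- On accidental unblinding of an investigator, site staff or a patient: "the unblinding will not be sufficient cause for the patient to be discontinued from study treatment or excluded from study analyses".
- On what then happens to such a case: it is recorded in the eCRF and "evaluated by the DSMC for appropriateness of inclusion in the study analysis".

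Emergency code breaks have their own paragraph in 4.2 and are not part of this review step.

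Section 4.1 adds, on the DSMC's access to results: "The interim analysis will be conducted for futility and efficacy and will be reviewed by the DSMC". Section 12.3.2 defines the modified intent-to-treat efficacy set: "Subjects who have successfully undergone brachytherapy and received one dose of Q-Urol will be evaluable for response". It contains no exclusion for unblinding. Section 13.2.2 (primary endpoint) does not mention unblinding. Section 16.3 lists DSMC activities without any analysis-set decision, and refers to a separate DSM plan for the committee's roles. Section 15 gives the DSMC or compliance staff access to patient source documents.

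**The concern.** The default in 4.2 is inclusion. The sentence after it hands a case-by-case judgement to a body that knows the arm and has seen interim efficacy results. Nothing in the documents reviewed says on what grounds the judgement is made, whether it must be made before the interim or final analysis, or whether the committee must be masked to the patient's NIH-CPSI score. Nor do they say whether the analysis in question is the primary one or a supportive one.

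The primary endpoint is patient-reported and the comparison is a simple difference in means, so the analysis set should be fixed by rule and should not depend on a decision taken with knowledge of arm. If it does depend on such a decision, the error rate stated in 13.2.1 is no longer guaranteed. The adjustment promised there covers analyses done at a sample size other than planned; it does not cover selection by arm or outcome. Even if no harm is done, the sponsor would find it hard to answer, after the event, a question about who was left out and why.

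**Working it through.** **1. The text.** The two sentences in 4.2 are compatible. The first rules out exclusion for unblinding alone; the second leaves room for exclusion on some further ground, which is not stated. Sections 12.3.2, 13.2.2 and 16.3 do not supply that ground. So the discretion exists, and the documents reviewed set no bounds on it.

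**2. The plan's own figures.** Inputs from 13.2.1: 21 then 70 patients per group; stop for futility if t < -1.16 and for efficacy if t > 2.85; at the end, "the treatment will be deemed efficacious at the final analysis if the t statistic has a nominal value greater than 1.67"; effect 0.5 SD. The statistic is taken as the pooled two-sample form, t = (mean of control - mean of treatment) / sqrt[s² (1/n_C + 1/n_T)]. With 400,000 simulated trials per scenario and normal outcomes with SD 1:

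| Quantity | Plan | Simulated |
|---|---|---|
| Type I error (one-sided) | 0.05 | 0.0502 |
| Power at 0.5 SD | 90% | 0.901 |
| Futility stop, null | 12% | 12.7% |
| Futility stop, alternative | 0.3% | 0.3% |
| Efficacy stop, alternative | 12% | 12.4% |

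The design reproduces closely enough to serve as a base.

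**3. Illustration of selective exclusion.** These inputs are assumptions, because the documents give no unblinding rate:

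- u patients per arm are accidentally unblinded, all among the 49 per arm recruited after the interim (70 - 21 = 49).
- Whoever decides can see patient-level scores.
- Unfavourable means a supplement patient above the pooled mean or a placebo patient below it (higher NIH-CPSI is worse).

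The final boundary stays at 1.67. One-sided type I error:

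| Rule | u = 1 | u = 2 | u = 4 |
|---|---|---|---|
| Unfavourable dropped with 25% probability, both arms | 0.0519 | 0.0531 | 0.0569 |
| Same, 50% probability | 0.0534 | 0.0573 | 0.0650 |
| Always dropped, supplement arm only | 0.0535 | 0.0575 | 0.0659 |
| Always dropped, both arms (worst case) | 0.0567 | 0.0643 | 0.0830 |
| All unblinded dropped whatever the outcome | 0.0504 | 0.0498 | 0.0510 |

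Monte Carlo standard error is at most 0.00044. Separate runs of these scenarios differ by about 0.001, so the 25% row for u = 1 and 2 is best read as 0.052 to 0.054.

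**4. Hand check of the 25% row.** For a standard normal score, dropping unfavourable values with probability p shifts a patient's expected contribution by p × 0.399. With p = 0.25 that is 0.0997. For u = 1 in each arm the difference in means shifts by 2 × 0.0997 / 70 = 0.00285. The standard error of the difference is sqrt(2/70) = 0.169, so t shifts by 0.00285 / 0.169 = 0.0169. The normal density at 1.67 is 0.0989, so type I error rises by about 0.0989 × 0.0169 = 0.0017, giving 0.0502 + 0.0017 = 0.0519. For u = 2 the rise doubles to 0.0033, giving 0.0535. This ignores the interim stops and agrees with the simulation.

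**5. Cost of a rule that drops all of them.** If unblinding is unrelated to outcome, power at 0.5 SD is 0.8967, 0.8935 and 0.8849 for u = 1, 2 and 4, against 0.901 with nobody dropped. The type I error in the last row of the table rests on the same condition.

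**The case against.** The best defence is that 4.2 already states the governing rule. Unblinding alone does not remove a patient, and 12.3.2 defines the efficacy set without such an exclusion. Dropping patients because of their scores would depart from the protocol, not apply it. The phrase about the study analysis need not mean the primary one, and the DSM plan cited in 16.3 may set criteria, timing and data access. The placebo is "identical in appearance to Q-Urol", so accidental unblinding may be rare. A review outside the study team also has a rationale when the unblinded person is a member of that team.

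Most of this stands, and it limits the point to a possibility that the text leaves open. It does not close the gap: the review step is written into the plan, it must be capable of changing something, and nothing available confines it to a supportive analysis or to decisions made without outcome data.

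A reader might infer that 4.2 contradicts itself; it does not. A reader might infer from section 15 that the DSMC would use NIH-CPSI scores in these decisions. Access to source documents makes that possible, but no passage says that scores are consulted, or that they are withheld. A reader might also take 0.083 as the trial's error rate. That needs four unblinded patients in each arm after the interim, sight of their scores, and a committee that always excludes in the supplement's favour; the documents support none of these.

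**Conclusion.** The point holds as a weakness of wording that permits arm-aware exclusions from the primary analysis; it does not show that any would occur. The size is unknown and probably small. With 1 or 2 unblinded patients per arm and 25% outcome-driven exclusion, type I error is about 0.052 to 0.054 against 0.050. That range rests on assumed counts, assumed access to scores, normal outcomes and no selection at the interim. No figure stated in the plan has to be corrected. If the unseen DSM plan sets criteria, timing and masking, what remains is to say which analysis 4.2 refers to. This is a cheap improvement, not a condition for the trial to be valid, and confidence is medium.

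**What to change.** In 4.2, delete the clause "evaluated by the DSMC for appropriateness of inclusion in the study analysis" together with the word that joins it to the recording step, and keep the eCRF record. Add that accidentally unblinded patients who meet the 12.3.2 efficacy-set definition stay in the primary efficacy analysis in their randomised arm.

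If the sponsor wants to see results without them, list in 13.2.2 a supportive sensitivity analysis that drops all such patients by rule. State its limit there: it is free of selection bias only if unblinding is unrelated to outcome. If unblinding followed poor scores or side effects in one arm, dropping those patients by rule could shift the result much as selective exclusion does.

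The cost is a short edit to 4.2 and, if the sensitivity analysis is wanted, an entry in 13.2.2. The DSMC loses case-by-case discretion. Sample size, data collection and the primary test do not change. The wording in 12.3.2 that refers to a dose of Q-Urol, and read literally leaves out placebo patients, is a separate point to be settled on its own.

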4.3 Number of Patients

The trial will enroll up to 70 patients to each arm, 140 patients total.

4.4 Number of Study Centers

This will be a single-center trial run at the Huntsman Cancer Institute at the University of Utah.

4.5 Study Duration

The study is projected to last for 3 years from the first patient on to the last patient end of treatment visit.

Version Date: 11APR2023

5 ELIGIBILITY CRITERIA

This eligibility checklist is used to determine patient eligibility and filed with the enrolling investigator's signature in the patient research chart.

Patient 1	No									
Patient'	s Initial	s: (L,F,M)								
5.1	Inclus	Inclusion Criteria								
	Yes/No (Response of "no" = patient ineligible)									
	5.1.1	Male subjects aged ≥ 18 years.								
	5.1.2	Men with histologically proven localized prostate adenocarcinoma, stage I – III (as defined by AJCC 8 th edition), who have selected treatment with brachytherapy with or without external beam radiation, with or without androgen deprivation therapy.								
	5.1.3	Fluent in speaking and reading English.								
	5.1.4	ECOG Performance Status ≤ 1 .								
	5.1.5	Adequate organ function as defined as:								
		• Hepatic:								
		o Total Bilirubin ≤ 1.5x institutional upper limit of normal (ULN)								
		○ $AST(SGOT)/ALT(SGPT) \le 3 \times institutional ULN$								
		• Renal:								
		 Estimated creatinine clearance ≥ 30 mL/min by Cockcroft-Gault formula: 								
		■ Males: $\frac{(140-age)\times weight[kg]}{serum\ creatinine\ \left[\frac{mg}{dL}\right]\times 72}$								
	5.1.6	Highly effective contraception for both male subjects and their female partners of childbearing potential throughout the study and at least 5 days after last study treatment administration if the risk of conception exists.								
	5.1.7	$\underline{{\text{Index}}\text{ (https://eprognosis.ucsf.edu/leeschonberg.php)}}$								
	5.1.8	Able to provide informed consent and willing to sign an approved consent form that conforms to federal and institutional guidelines.								

Version Date: 11APR2023

5.2 Exclusion Criteria

Yes/No (Response of "yes" = patient ineligible) 5.2.1 Baseline AUA symptom scores > 15. 5.2.2 Prior diagnosis of chronic prostatitis type II through IV. Subject has received systemic therapy intended for the treatment of 5.2.3 prostatitis (including herbal supplements) ≤ 14 days of starting study treatment. 5.2.4 Subject has received a fluoroquinolone antibiotic (e.g. ciprofloxacin, norfloxacin, ofloxacin levofloxacin, etc.) ≤ 3 days of starting study treatment. 5.2.5 Subject is actively on anti-inflammatory medications for other medical conditions, unless approved by PI. Subject has undergone transurethral resection of the prostate (TURP). 5.2.6 5.2.7 Patients with a prior or concurrent malignancy whose natural history or treatment has the potential to interfere with the safety or efficacy assessment of the investigational regimen. History of irritable bowel syndrome, chronic fatigue syndrome, 5.2.8 fibromyalgia, and interstitial cystitis-bladder pain syndrome (IC/BPS). 5.2.9 History of symptomatic hypotension, falls, or syncope **5.2.10** Chronic hypoglycemia requiring hospitalization. **5.2.11** Actively abusing alcohol or drugs The subject has uncontrolled, significant intercurrent, or recent illness including, but not limited to, the following conditions: • Congestive heart failure Diabetes Pulmonary artery hypertension Any clinically significant condition that requires therapy with diuretic medications for any indication other than the management of hypertension. Other clinically significant disorders that would, in the opinion of the

treating investigator, preclude safe study participation.

Short Title: Q-Urol								
Version Date: 11API	R2023							
5.2.13	Known prior severe hyper component in its formulations (N	•	C 1	duct or any				
5.2.14	Known allergy to pineapp	le or pineap	ple containing produc	cts.				
5.2.15	washout period of prohibited me	Subjects taking prohibited medications as described in Section 7.3 A shout period of prohibited medications for a period of at least 5 half-lives or clinically indicated should occur prior to the start of treatment.						
I certify that thi study.	s patient meets all inclusion and	d exclusion	criteria for enrollm	ent onto this				
Investigator Sign	nature	Date	 Time					

Version Date: 11APR2023

5.3 Recruitment Strategies

Potential patients will be identified by Investigators in the setting of their outpatient clinics.

6 STRATIFICATION FACTORS

Patients will be stratified by prior use of alpha-blockers for prostate related condition (yes, no) and the dose of brachytherapy: high dose rate (HDR) or low dose rate (LDR).

7 TREATMENT PLAN

7.1 Administration Schedule

Patients will undergo Low Dose Radiation (LDR) brachytherapy with or without External Beam Radiation Therapy (EBRT) or High Dose Radiation (HDR) brachytherapy with EBRT. When LDR is used as monotherapy the isotope will be PD-103 prescribed at 125 Gy, when used as a combined modality with EBRT, the LDR brachytherapy will precede the EBRT, the isotope used will be PD 103 prescribed at 100Gy. HDR monotherapy will not be performed. The HDR + EBRT regimen will be a single fraction of Iridium-192 prescribed at 15Gy and will precede the EBRT. When EBRT is combined with LDR or HDR, the EBRT will only occur after the completion of the study drug regimen and toxicity evaluations for the primary endpoints.

On the day of but after brachytherapy, patients will self-administer two Q-Urol or placebo capsules by mouth with food twice daily. Doses should be taken at about the same time every day (\pm 4 hours) and recorded on the patient's dosing diary. Doses missed outside of the dosing window should not be made up but rather patients should be instructed to take their next dose at their regularly scheduled time.

7.2 O-Urol and Identical Placebo

7.2.1 How Supplied, Stored, Packaged, and Labeled

Q-Urol will be provided by Farr Laboratories. Q-Urol will be provided as 375 mg proprietary blend and 37.5 mg calcium capsules for oral administration. They should be stored at room temperature, away from heat, moisture, and direct light.

Placebo capsules, which do not contain the active ingredients of Q-Urol, will be compounded by the Investigational Drug Services Pharmacy at Huntsman Cancer Institute and will be identical in appearance to Q-Urol.

The Investigator, or an approved representative, will ensure that all investigational products are stored in a secured area with controlled access under required storage conditions and in accordance with applicable regulatory requirements.

According to Farr labs, the Q-Urol is manufactured in laboratories with Current Good Manufacturing Practice regulations enforced by the FDA. In addition, Farr Laboratories ensures consistency and purity via the following measures:

Version Date: 11APR2023

 Ensures that the Certificates of Analysis (CofA's) are in compliance with the United States Pharmacopeia (USP) standards on Identification and Purity Controls

- Monitor manufacturing and quality control product documentation
- Conduct laboratory testing on Finished products for Microbio, Heavy Metals, and Residual Solvents

7.2.2 Preparation and Administration

Subjects will be provided enough Q-Urol/placebo for a full six weeks of treatment at the time of brachytherapy. Subjects will be instructed to self-administer the medication at home orally twice daily (every 12 hours \pm 4 hours) with food. Subjects should begin dosing the evening after brachytherapy placement. Subjects should not take extra medication for any reason nor should they re-administer in the case of vomiting after administration. If a dose is missed outside of the dosing window, the dose should not be made up.

7.2.3 Accountability and Compliance

Information pertaining to study drug compliance (i.e., date, time, and dose) will be recorded by patients on the drug diary (see Appendix 6) and recorded in the corresponding electronic case report form (eCRF) by the study team. A member of the study team will review patient drug compliance and provide patient re-education as required. Any reason for non-compliance will be documented in the subject's research chart and the corresponding eCRF. At the discretion of the principal investigator, a subject may be discontinued from the trial for non-compliance with study visits or study drug.

Subjects will be required to return any unused medication or empty bottles at the end of study therapy. Excess or unused study drug should be returned to the investigative site for accounting and destroyed in accordance with GCP after drug accountability has been performed. The total number of capsules dispensed, returned, and documented as taken will be reconciled to support drug accountability. Treatment compliance will be calculated and recorded for the study drug. It will be recorded as a percentage defined as the number of doses taken divided by the expected number of doses taken multiplied by 100%.

